2.4.5 Economic analysis

Data from the observational studies will be used to determine the additional staffing costs associated with any proposed observation schedules. Incremental costs associated with proposed new protocols will be compared with both current protocols and current practice (estimated using observation frequency and compliance with current protocols from wards in sites using electronic recording). We will estimate daily and annual staffing costs associated with taking observations for

- i. Current observed observation frequency
- ii. Current planned observation frequency (current protocol)
- iii. Alternative observation schedules (alternative protocol)
- iv. Alternative observation schedules allowing for non-compliance.

Current observed observation frequency and planned observation frequency will be determined by records of complete and omitted vital signs observations. The alternative observation frequencies will be estimated by using current vital signs observations to simulate observations schedules according to the new protocols.

The cost of each observation regimen will be estimated by multiplying the cost of staff time (hours) associated with the regimen (length X number of observation estimated from the profile of NEWS scores on similar wards) by the appropriate unit

costs derived from current (at time of study) Agenda for Change pay bands, adjusted for on-costs and overheads (see table below for examples; reference years will be the latest available updates) following established methods [50].

Costs				Source
RN hours	Employed / Bank staff	Band 5 Band 6	£35 £44	CURTIS, L. & BURNS, A. 2016. Unit Costs of Health and Social Care 2016,
HCA hours	Employed / Bank staff	Band 2 Band 3	£22 £28	Canterbury, PSSRU, University of Kent. [50]

We will initially assume that the grade of staff taking observations is unchanged, so if 50% of observations are currently undertaken by Band 2 HCAs we will assume 50% of observations under the new regime are also undertaken by Band 2 HCAs. The estimate of staff costs will be weighted accordingly.

We will estimate costs for regimens assuming full compliance and partial compliance based on currently observed rates. As we know that compliance with vital signs observations is highly correlated with the scheduled frequency we will use adjusted and unadjusted rates such that (for example) we assume that 80% of all observations are taken under both old and new regimes (unadjusted) or we stratify estimated compliance by observation frequency so that (for example) 100% of 12 hourly observations are taken whereas 50% of 4 hourly observations are taken. As a secondary analysis we will also consider changes in staff skill mix, for example if a new regime increases the number of observations then we might assume that all additional observations are undertaken by Band 2 HCA.

Cost differences will be calculated by determining the difference in cost between two regimes. Marginal consequences will be estimated differences in resource use (time and grade/type of staff conducting observations and follow-up). We will derive estimates of possible benefits (e.g. reduced mortality, length of stay in ICU) by relating the time of detection of deterioration associated with a given monitoring protocol, to coefficients derived from published studies that report the benefits of early detection and/or increased frequency of observations[51]–[54]. The incremental benefits of each proposed protocol will be compared to the incremental staffing costs and a cost per life saved estimated. We will also estimate QALYS on the assumption that life expectancy and quality of the 'lives saved' will be similar to that of the group of patients who died using standard estimates of QALE adjusted for patient demographic factors[55]. If reductions in ICU admissions, hospital stay or other resource use are identified as outcomes these will also be considered in the estimated cost differences. These will be costed using Department of Health Reference Costs 2015-2016 (or latest available update).

All variables included in the economic analysis are estimated subject to (parameter) uncertainty, while model type, the models and assumptions made in building them are subject to methodological and structural uncertainties. We will address methodological and structural uncertainty through scenario analyses testing the robustness of the results to model type, scope and other key structural assumptions. Parameter uncertainty will be addressed through deterministic sensitivity analyses

(using statistically-derived limits for input variables, where possible), scenario analyses (using alternative data sources, if available) and (data and model permit) probabilistic sensitivity analysis. The estimates of cost effectiveness derived in this way will further inform the assessment of feasibility of the observation protocol. While such estimates would need validating in a trial, this preliminary modelling will inform judgements as to whether a given monitoring protocol has the potential to be judged cost-effective

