2.2.2.2 Implications for staff resources

Whereas under-observation can delay the opportunity to detect patient deterioration and initiate remedial treatment[8], [9], over-observation uses valuable nursing resources that could be better deployed to other essential aspects of patient care. Indeed, compliance with current monitoring protocols is often poor, with many observations missed or delayed[11]–[14]. This is particularly evident at night[12], [23], [24], when staffing is at its lowest. Preliminary results from our current HS&DR "Missed Care" study (ISRCTN: 17930973) show that compliance with vital signs observations is significantly (p<0.05) associated with the level of available nursing staff. Estimates of the time required to take observations are scarce, but a survey of 2917 registered nurses across 46 acute hospitals in England showed that one-third had felt unable to undertake all necessary patient surveillance due to lack of time on their last shift[15]. However, even when staffing is sufficient, there are valid clinical reasons why nursing staff will deviate from protocols. Therefore, it is essential to have a monitoring protocol that is achievable on the ward and does not compromise other aspects of care.

With this in mind, and by adapting techniques from our previous work[15], [25], [26], part of this study will be a prospective observation of recording vital signs across a range of wards. This will allow us to understand better the impact on staff workload and factors that might affect compliance with patient surveillance.

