2.2.3 Evidence explaining why this research is needed now

Current UK professional guidance[1], [2], [13], [27], [28] suggests that the frequency of monitoring should be determined by some measure of physiological disturbance. One such measure is the National Early Warning Score (NEWS)[5], which provides a simple integer score based on the degree to which a patient's vital signs are outside the normal range. There is now some evidence to support its ability to predict a patient's risk of adverse outcomes[5], [7], [29]–[31], albeit with high false positive rates. However, we were unable to identify any large studies to support the vital sign monitoring intervals suggested by the original guidelines from the Royal College of Physicians[1]. For example, the NEWSDIG recommended at least hourly observations for any patient with acuity of NEWS 5 or more. To put this recommendation into context, the surveillance protocol for patients with NEWS 5 at Portsmouth Hospitals is 4 hourly, and there is only 50-70% compliance with protocol at this frequency, for a number of potentially legitimate reasons. Without an evidence base, compliance is seen mainly as a superficial mechanistic proxy for quality of care.

As discussed above, under-observing patients runs the risk of missing early signs of deterioration, but taking repeated measurements in patients is also a drain on valuable staff resources. Obtaining vital sign measurements is one part of the "chain of prevention" [32], necessary to effectively recognise and manage the deteriorating patient. For example, a national enquiry into patients who underwent cardiopulmonary resuscitation in hospital [8] showed 20-40% did not have a clear monitoring plan in the 48 hours prior to the event, despite over 70% having significant physiological abnormalities. It is therefore crucial for safety that patients' observations are correctly targeted and escalated appropriately. However, this must be balanced with other negative consequences. For example, obtaining observations can be disturbing for patients [33] and might be associated with negative health outcomes if they contribute to sleep disruption [24], [34]. Monitoring protocols that demand observations when staff deem it futile in particular situations, in particular if these may have adverse effects, risks delegitimising the EWS protocol.

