2.4.1.3 Data collection and sampling

Data for the retrospective study will be derived from repositories of vital signs obtained using the Vitalpac™ (PHT) and SEND (OUHT) systems, both of which enable nursing staff to record physiological measurements at the bedside using electronic devices[41], [42]. At both sites, we will obtain all measurements of heart rate, respiratory rate, systolic and diastolic blood pressure, temperature, oxygen saturations, current oxygen therapy (device and flow rate) and level of consciousness (on the AVPU scale). At Portsmouth, Vitalpac™ implements the National Early Warning Score (NEWS)[1], which is used to recommend the time to the next observation, based on a minor modification of guidelines from the Royal College of Physicians[1]. At Oxford, SEND uses the Centile Early Warning Score (CEWS)[43] to recommend the time to the next observation. The recommended time to next observation used in each system will also be collected, as it could impact our modelled risk estimates.

Vital signs data will be linked to the local patient administration, laboratory, theatre management, intensive care and cardiac arrest databases. This will provide information on patient demographics (age, co-morbidities), in-hospital mortality, unanticipated ICU admissions (i.e. those resulting from deterioration on the wards) and cardiac arrests. In this project, we expect to extract vital signs data (approximately 6 million observations from 200,000 patient admissions) from

completed admissions from both sites over a 10-year period (2010-2020) from PHT¹. A compatible data set from OUHT will be extracted from a 4-year period (2017-2020) in which the SEND system had maximal coverage of OUHT².

We will also extract blood test results from laboratory systems to allow us to better model the risk of adverse outcomes and permit sub-group identification (e.g. patients with chronic renal failure).

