2.4.1.4 Data analysis

Intermittent observations of vital signs show some specific features that should be properly accounted for in any modelling framework. They are longitudinal in nature, i.e. multiple observations are taken over the same sample unit (patients) over time, and are multivariate as multiple variables (e.g. pulse, blood pressure) are jointly measured at each observation time. These data also show serial dependence and high correlation between measurements within patients. A natural way to account for these features is to use State Space Models (SSMs), as they provide a framework of flexible time-dependent models. SSMs cast multivariate distributions (see [44] for a review), accounting for the serial dependence, heterogeneity between patients, and transitions between states that depend on other covariates. We will use this modelling approach to estimate changes in vital signs over time and the probability of adverse events (e.g. in-hospital mortality, unanticipated ICU admission, cardiac arrest).

Our reference modelling setting will be the multivariate Hidden Markov Model (HMM)[45], a well-known type of SSM. Its use is justified by its versatility and mathematical tractability:

- the availability of all moments
- the likelihood computation is linear with respect to the number of observations;
 the marginal distributions are easy to determine and missing observations can be handled with minor effort
- the conditional distributions are available, outlier identification is possible, and forecast distributions can be calculated

For vital signs data collected during routine monitoring on the ward, there are additional clinical processes that have the potential to introduce bias our analysis. Firstly, these data have been collected in the context of existing monitoring protocols, where the time to the next observation is determined by an early warning score (NEWS[1], [5], Portsmouth; CEWS[43], Oxford). Secondly, previous work[12] by our group and others shows that in practice, nursing staff often undertake "observation rounds", in the early mornings and evenings. These observations result in deviations from the patient-specific schedule dictated by the early warning score. Thirdly, there will be observation sets taken when patients report additional symptoms or are deemed to "look unwell"; information that will not captured in available variables in our data set.

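### Compliance with new schedules may vary only by scheduled frequency, which the score itself sets, so the planned scenarios need not bracket realistic workload when a score is given a different interval

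*Protocol*

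**What the plan says.** Protocol 2.4.5 costs four regimens. Item iv, the alternative schedules allowing for non-compliance, is the realistic workload estimate. Its compliance inputs come from current practice: "We will estimate costs for regimens assuming full compliance and partial compliance based on currently observed rates". Two partial-compliance versions are described:

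- Flat: "we assume that 80% of all observations are taken under both old and new regimes (unadjusted".
- Adjusted: "we stratify estimated compliance by observation frequency so that (for example) 100% of 12 hourly observations are taken whereas 50% of 4 hourly observations". The stated ground is a correlation: "As we know that compliance with vital signs observations is highly correlated with the scheduled frequency".

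Elsewhere the protocol names other influences on whether a set is taken:

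- Section 2.4.1.4 says that the data arise under protocols "where the time to the next observation is determined by an early warning score" (NEWS at Portsmouth, CEWS at Oxford).
- Section 2.2.3 reports compliance for a score group. For NEWS 5 at Portsmouth the surveillance protocol "is 4 hourly, and there is only 50-70% compliance with protocol at this frequency".
- Section 2.2.2.2 says of missed or delayed sets: "This is particularly evident at night". It also links compliance to staffing.
- Section 2.4.1.3 extracts the scheduled interval for the risk model: "The recommended time to next observation used in each system will also be collected, as it could impact our modelled risk estimates".

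Section 2.4.4 then sets out to propose different schedules according to patients' current acuity.

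**The concern.** Because the score sets the interval, observed compliance at 4-hourly is the compliance of the scores currently placed on 4-hourly, and likewise at 12-hourly. The correlation in 2.4.5 cannot tell whether staff respond to the interval, to how ill the patient is, or to both. This does no harm while scores keep their intervals. A new protocol that gives a score a different interval breaks the link from which the rate was estimated.

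The authors treat score-driven intervals as a possible source of bias in the hidden Markov model, and they put time of day into that model. Neither consideration reaches the compliance step in 2.4.5. At stake is item iv, which feeds the incremental staffing cost, the cost per life saved and the feasibility judgement. The protocols most exposed are those that depart furthest from current practice.

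**Working it through.** The 100%, 50% and 80% rates are labelled as examples, so there is no planned result to reproduce. The check asks whether the three planned scenarios cover the case in which compliance follows the score. The interval changes below only illustrate the arithmetic; they are not suggestions for care.

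**Inputs.** From 2.4.5: 100% at 12-hourly, 50% at 4-hourly, 80% flat, and full compliance. From 2.2.3: 50-70% for NEWS 5 at 4-hourly.

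**Formula.** Sets taken per patient-day = (24 / interval in hours) × compliance. Scheduled sets are 24/12 = 2 and 24/4 = 6.

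**Score-5 patients, 4-hourly to 12-hourly**

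| Rule | Sets taken at 12-hourly |
|---|---|
| Full compliance (planned) | 2 × 100% = 2.0 |
| Frequency-stratified (planned) | 2 × 100% = 2.0 |
| Flat (planned) | 2 × 80% = 1.6 |
| Follows score | 2 × 50% = 1.0 to 2 × 70% = 1.4 |

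The planned range is 1.6 to 2.0, and the score-following range lies wholly below it.

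Change against observed current practice (item i):

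- At 50%, current practice is 6 × 50% = 3.0. Planned changes are 2.0 − 3.0 = −1.0 and 1.6 − 3.0 = −1.4; score-following is 1.0 − 3.0 = −2.0.
- At 70%, current practice is 6 × 70% = 4.2. Planned changes are 2.0 − 4.2 = −2.2 and 1.6 − 4.2 = −2.6; score-following is 1.4 − 4.2 = −2.8.

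**Low-score patients, 12-hourly to 4-hourly**

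| Rule | Sets taken at 4-hourly |
|---|---|
| Full compliance (planned) | 6 × 100% = 6.0 |
| Flat (planned) | 6 × 80% = 4.8 |
| Frequency-stratified (planned) | 6 × 50% = 3.0 |
| Follows score | 6 × 100% = 6.0 |

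Here full compliance equals the score-following value, so the planned range covers it.

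**Why the two moves differ.** If a group's compliance is below the ward average, and below the rate seen at the sparser interval, its own rate is lower than all three planned rates. Moving it to that interval therefore gives fewer sets than any planned scenario. In the other direction, no group rate can exceed 100%, so full compliance is always an upper bound.

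**Night.** Assume that 2 of 6 four-hourly slots fall at night and that average compliance is 50%. Day compliance is then (6 × 50% − 2 × night rate) / 4. Night rates of 10%, 20%, 30% and 50% imply day rates of 70%, 65%, 60% and 50%. A schedule keeping only the 4 day slots yields 2.8, 2.6, 2.4 or 2.0 sets, against 4 × 50% = 2.0 from the frequency rate. The protocol gives no night rate and no night share, so this shows only the mechanism.

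**The case against.** Four stronger readings are tempting, and the protocol does not support them.

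- A reader might infer that workload is predicted from frequency alone. Frequency stratification is one of three scenarios; full compliance and a flat rate are also planned.
- A reader might infer a fourfold error in incremental cost from the low-score example: +4.0 sets if compliance follows the score (2.0 to 6.0) against +1.0 under the frequency rule (2.0 to 3.0). But +4.0 is also the planned full-compliance increment (2 to 6).
- A reader might infer that the predicted workload is wrong. The protocol gives no compliance by score within an interval and none by hour. If the interval truly drives compliance, the planned rule is right.
- A reader might infer that night misses are ignored. A frequency-specific rate already contains the night misses at that frequency. Hour due matters further only if a new schedule changes the share of sets due at night.

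The non-bracketed case also depends on the comparison. When old and new regimens are both costed under the same rule, the score-5 changes at 50% are −1.0 (frequency), −3.2 (flat, 4.8 to 1.6) and −4.0 (full, 6 to 2). The score-following −2.0 lies inside that range. The gap is in the absolute level and in the change from observed practice. Section 2.4.5 does name current practice as a comparator, so this part of the point stands.

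Finally, 2.4.5 promises scenario analyses on key structural assumptions and says that the estimates would need validating in a trial. The promise does not mention compliance. Finer stratification could sit in an analysis plan, but here the protocol itself names frequency as the stratifier.

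**Conclusion.** The point holds as a possible bias, not a demonstrated one. Compliance is carried to new schedules on frequency only, although the score sets frequency, and the planned scenarios need not bracket the consequence. In the illustrative score-5 case, 1.0 to 1.4 sets are taken per patient-day against 1.6 to 2.0 in every planned scenario. Relative to observed practice at 50%, the change is −2.0 against −1.0 to −1.4. For low-score patients moved to a denser schedule, the plan already covers the score-following value.

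These sizes rest on the protocol's example rates, on its 50-70% for NEWS 5, and on the extreme assumption that compliance follows the score entirely. The real size and direction are unknown. This is a cheap improvement to item iv; it does not invalidate the economic analysis.

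**What to change.** In 2.4.5, for item iv:

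1. Estimate compliance from the electronic records by recommended interval and score band together. Add time due (day or night) where a new schedule changes the share of sets due at night.
2. Apply these rates in the schedule simulation.
3. Add a scenario in which compliance follows the score, beside the frequency-stratified one. Where an interval-score combination was not observed, report the two as a range.

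The use of NEWS at one site and CEWS at the other may help separate score from interval, but it is confounded with hospital. The before/after period at Portsmouth helps only if intervals changed then, which the protocol does not say. Many interval-score cells may be sparse, so the range in step 3 may be the main output.

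The cost is some extra analysis of data already being extracted, and a wider stated range. No new data collection is needed.

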2.3 Research question/aim(s)

This study aims to recommend subsequent observation frequencies based on the risk of missing significant deterioration in the intervening period. Prospective observations of nursing staff will allow us to quantify the cost of different monitoring protocols, based on varying thresholds of risk. We will exploit a large database of vital sign observations, laboratory data and diagnostic codes from 2 acute hospitals (Oxford and Portsmouth), supplemented by prospective observation in 4 hospitals to estimate nursing workload associated with these observations.

The objectives are to:

- Develop a data warehouse of linked admission records with information on patient demographics, vital signs observations and adverse events (cardiac arrests, unanticipated ICU admissions, in-hospital mortality).
- Estimate the rate of clinically significant changes in vital signs over the course of patients' admission.
- Explore the relationship between vital signs and adverse outcomes over time.
- Determine the extent to which relationships between the time to deterioration and risk of adverse outcomes vary across different patient groups (e.g. medical and surgical; elective and non-elective surgical patients; age; co-morbidities).
- Organise stakeholder (nurse, doctor, patient) events to identify additional factors relevant for selecting an optimal monitoring protocol.
- Undertake prospective observations of nursing care to estimate the time taken to obtain and respond to vital signs observations, using techniques adapted from previous work[26] and our HS&DR funded "CLECC" study[25].
- Derive a set of simple monitoring protocols by identifying any threshold effects between the risks over time predicted by our models.
- Use estimates from our observational work to model the marginal costs and consequences for all protocols with better or equal performance to the current protocols at Portsmouth and Oxford for detecting deterioration.
- Use results to inform design of a prospective clinical trial.

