2.4.3.3 Observation session

Observations will be undertaken by one or more trained researchers, who will act as non-participant observers. They will position themselves to be able to discreetly observe a group of patients whose vital signs observations will fall due, or else discreetly shadow a nurse who is about to undertake a vital signs observation round. We will adapt tools and techniques from the HS&DR funded 'CLECC' study [25] and Wong et al.[26] Data will be recorded on a tablet device using software designed for recording nurse patient interactions on wards (QITool) with records taken at both the session level and the 'interaction' level (in this case a set or group of vital signs measurements). For each observation session we will record the number of patients and the number and grades (RN band 5 and above, HCA and other assistant staff

band 1-4) of all nursing care staff on the ward. For each patient whose vital signs are recorded we will assign a session-specific identifier and record basic details that can be discerned from distant observation, such that would be available to any visitor to the ward (for example position and the presence of visitors). The type of staff taking vital signs measurements will be recorded and categorised (e.g. registered nurse, care assistants).

We will record start and finish times for both vital signs rounds and individual vital signs measurements. For a vital signs 'round' an interaction record will be opened with a start time recorded when the nurse begins to assemble the necessary equipment and ended when the nurse moves away from the patient bed space and engages on another task (i.e. other than taking vital signs measurements from the next patient) unrelated to vital signs measurements. Therefore, each set vital signs measurements will be clustered with a vital signs 'round' which will include one of more sets of vital signs measurements. Observation sessions will continue for 2 hours with observer discretion to extend the session if the required number of vital signs measurements have not been recorded.

Observers will not intervene in care but should they observe practice that risks causing the patient harm they will alert the nurse in charge.

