2.4.4 Generating putative monitoring protocols

In the later stages of the project, the findings from the observational studies and stakeholder consultations will be brought together to create and validate protocols. The primary outcome of WP2 will be a data-driven schedule for monitoring patients'

vital signs, based on their current acuity. Using estimates from our state-space models we will explore the following:

- 1. Given a level of physiological abnormality what is the average chance that this value will be higher at any given point of time in the future?
- 2. Given a level of physiological abnormality, what is the average chance that an adverse event will occur at any given point of time in the future?

We will explore grouping patients using early warning scores (e.g. NEWS, CEWS). We aim to identify points in time where there is a significant risk that patients' vital signs have changed adversely. We will manually inspect these to look for threshold effects across time. For example, for low-acuity patients who deteriorate (i.e. increase in acuity), what is the earliest point in the future that this could be detected? A limitation of the study is that we can only explore average rates of deterioration, as we do not have access to data on interventions or individual diagnoses. However, we will explore how our estimates change in subsets of patients (e.g. elective surgery, emergency surgery and medicine). Exploring the data in this way will permit us to propose different monitoring schedules, designed to increase the likelihood that a new vital signs observation picks up deterioration if and when it happens.

We will also undertake a variety of computer simulation studies, where estimates from our models are used to simulate the performance of current monitoring protocols (e.g. those proposed by the RCP[1]) and our new ones. This will allow us to quantify: (a) the number of observations required; and (b) the risk that deterioration will be missed.

The estimates obtained from WP3 will then be used to model the marginal costs and consequences for all protocols whose performance is equivalent to or exceeds that of the current NEWS protocol for detecting deterioration. In addition, we will model potential reductions in mortality and changes in ICU use (e.g. admission/acuity at admission/length of stay) associated with improved detection. Finally, stakeholders will be consulted to review the protocols and comment on their likely effectiveness.

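### Section 2.4.5 costs ICU use, hospital stay and other non-staff resources only when they fall, so a protocol that detects more and raises such use would look cheaper than it is

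*Protocol*

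**What the plan says.** **Non-staff resources.** Section 2.4.5 sets the rule: "If reductions in ICU admissions, hospital stay or other resource use are identified as outcomes these will also be considered in the estimated cost differences". Such items are then priced at national reference costs. Section 2.4.4 describes the modelling that feeds it: "we will model potential reductions in mortality and changes in ICU use (e.g. admission/acuity at admission/length of stay) associated with improved detection".

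**Staff time.** Section 2.4.5 also states: "Marginal consequences will be estimated differences in resource use (time and grade/type of staff conducting observations and follow-up". The staffing cost of a regimen is staff hours times unit cost, with hours given as "length X number of observation estimated from the profile of NEWS scores on similar wards".

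**Time study.** One objective in section 2.3 is to "estimate the time taken to obtain and respond to vital signs observations", and section 2.2.3 promises workload estimates for both recording and responding. Under section 2.4.3.3 the record of a round is "ended when the nurse moves away from the patient bed space and engages on another task"; the sentence goes on to limit this to tasks that have nothing to do with vital signs. Section 2.4.3.6 defines two estimators, both of time per set. It says that associated actions within rounds are recorded, concedes that actions outside rounds cannot be, and will ask stakeholders whether an allowance should be added.

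**Value of lives saved.** Section 2.4.5 assumes that those saved would have had life expectancy and quality like those of the patients who died, "using standard estimates of QALE adjusted for patient demographic factors[55". Section 2.4.1.3 lists co-morbidities among patient demographics.

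**The concern.** An incremental cost is a net quantity, so each resource should enter with whatever sign it takes. The rule in 2.4.5 is conditional on the sign being favourable. Finding more deterioration, or finding it earlier, can avert ICU stays, but it can also bring about transfers that would not otherwise have happened. Section 2.4.4 leaves both directions open; 2.4.5 gives a costing rule for only one.

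Two related gaps concern the same comparison. The staffing formula depends on how many sets are taken, not on how many alerts they raise. And the QALY denominator rests on an adjustment whose content is not clear.

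At stake is the judgement, at the end of 2.4.5, of whether a schedule might prove cost-effective. That judgement is also meant to inform the assessment of feasibility.

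**Working it through.** The protocol gives no cost-effectiveness figure to reproduce. The check sets the sections side by side and then illustrates the direction of each gap. Unit costs of £35 per hour (Band 5) and £22 per hour (Band 2) come from the table in 2.4.5. Every other input below is an assumption.

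**1. Non-staff resources**

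| | Fall in use | Rise in use |
|---|---|---|
| Modelled (2.4.4) | yes | yes |
| Costed (2.4.5) | yes | no rule |

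Let S be the incremental staffing cost, R the value of reductions and I the value of increases (for instance, shorter hospital stay alongside more ICU admissions).

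- As written: S − R. Net: S − R + I.
- Set S = 100.
- R = 0, I = 20: 120/100 = 1.20. R = 0, I = 40: 140/100 = 1.40.
- R = 40, I = 20: 80/60 = 1.33. R = 40, I = 40: 100/60 = 1.67.

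For scale, take one uncounted ICU stay at £3,000 to £6,000 (assumption). £3,000/£22 = 136 Band 2 hours and £6,000/£22 = 273 hours. At 5 minutes per set (assumption) that is about 1,640 to 3,270 sets of observations.

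**2. Response work**

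Take two schedules with the same number of sets and the same staff mix, one raising more alerts. The formula in 2.4.5 gives them the same staffing cost. Add a response term: share of sets that lead to a response × Band 5 rate × minutes/60.

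- 5% of sets, 20 minutes: 0.05 × £35 × 20/60 = £0.58 per set.
- 10% of sets, 20 minutes: 0.10 × £35 × 20/60 = £1.17 per set.
- The difference of £0.58 compares with a 5-minute set at £35 × 5/60 = £2.92 (Band 5) or £22 × 5/60 = £1.83 (Band 2), that is 20% or 32%.

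The assumptions allow a wide range. At the low end, 5% of sets at 10 minutes adds £0.29 to a 7-minute Band 5 set of £4.08, or 7%. At the high end, 20% at 30 minutes adds £3.50 to a 3-minute Band 2 set of £1.10, or 318%. Any response done within a round is already in the recorded round time, so these overstate the gap to that extent. The retrospective data cannot supply the missing time, because 2.4.4 says that data on interventions are not available.

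**3. QALE**

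Cost per QALY = C/(L × Q), where C is incremental cost, L lives saved and Q the QALE per life. If the true value is a fraction f of the one used, cost per QALY is multiplied by 1/f: f = 0.75 gives 1.33, f = 0.50 gives 2, f = 0.25 gives 4. Cost per life saved is C/L and contains no Q.

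**4. Which schedules are affected**

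Section 2.4.4 carries forward protocols that match or exceed the current NEWS protocol in detection. One that exceeds it can raise transfers and alerts. One that matches it with fewer observations has no gain in detection to drive a rise, and no lives saved for QALE to inflate.

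**The case against.** The text is milder than a quick reading suggests, and four stronger inferences fail.

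- A reader might infer that only reductions in any resource are costed. Extra staff time is costed throughout 2.4.5, and its definition of marginal consequences names differences in follow-up staffing. The one-way rule covers only ICU use, stay and other non-staff items.
- A reader might infer that response work is not timed. A task related to vital signs does not by itself close the round record, in-round actions are recorded, and work outside rounds is acknowledged, with a possible allowance and sensitivity analysis. The document does not fix how that allowance would scale.
- A reader might infer that lives saved are valued at a general-population norm. The protocol's own use of demographics includes co-morbidities, so the wording is ambiguous rather than wrong, and an analysis plan could settle it.
- A reader might infer that all three gaps lower both ratios for every new protocol. QALE does not enter cost per life saved, schedules with equal detection need not gain, and the observer effect in 2.4.3.5 may lengthen timed measurements, which works against schedules with more observations.

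It is also fair that 2.4.5 never forbids costing an increase, plans scenario analyses in general terms, and calls the modelling preliminary and in need of validation in a trial.

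These points narrow the concern without removing it. No sentence brings an increase into the cost difference, none of the planned scenarios names it, and varying parameters under a one-signed rule leaves the rule one-signed.

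**Conclusion.** The point holds for non-staff resource use. Sections 2.4.4 and 2.4.5 do not agree, and 2.4.5 followed literally understates the incremental cost of any schedule that increases detection and thereby ICU use or stay. Whether any schedule would do so, and by how much, cannot be established from the document. The ratios of 1.2 to 1.67 show only what follows if the uncounted increase is 20% to 40% of incremental staffing cost, with savings of nil or 40%.

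Two secondary points hold in limited form. The gap in response work is confined to work outside rounds and to the lack of an alert-driven cost term, set against an objective that promises more. The QALE point is a request for clarification and bears on cost per QALY alone.

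**What to change.** **Main change, section 2.4.5.** Let the sentence on non-staff resources open with increases and decreases, and state that the net change always enters the cost difference at reference costs, whatever its sign. This brings it into line with 2.4.4.

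**Response work.** Either add a sensitivity analysis that costs, for each regimen, the simulated number of alerts times a range of response times drawn from the stakeholder work, or restate the objective in 2.3 and the promise in 2.2.3 as time to obtain observations plus in-round actions.

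**QALE.** State whether the adjustment includes co-morbidity, and name one reduced-QALE scenario. A mortality multiplier in the base case is not needed; its value would be a debatable choice.

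**Cost.** A few sentences, one or two model parameters and no new data collection. The drawback is that schedules with higher detection may show less favourable cost-effectiveness figures.
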